6.5.5 Efficacy Analyses

All efficacy variables derived from tumor imaging and response assessments will be determined using RECIST v1.1 and irRECIST. The primary analyses of tumor related efficacy variables will be performed using objective disease responses definitions based on RECIST. Exploratory analyses will be performed separately using objective disease responses definitions based on irRECIST.

6.5.5.1 Primary Efficacy Variable and Analysis

The ORR is defined as the proportion of subjects with best overall response (BOR) of partial response (PR) or complete response (CR) according to RECIST v1.1. The proportion of subjects with ORR in the EAS, along with a 95% CI based on the Wilson Score interval, will be reported. Analyses of ORR described above may be repeated in FAS, treating missing BOR as a non-responder. Objective disease response at each visit and best overall response will also be summarized using the EAS.

6.5.5.2 Secondary Efficacy Variables and Analyses

Secondary efficacy variables in the study include:

Disease control rate (DCR) defined as the percentage of subjects with BOR of CR, PR, or SD. The analysis of DCR will be performed using the EAS and conducted in the same manner as ORR.

Progression-free survival (PFS) defined as time from first dose of study drug to first documentation of disease progression (per RECIST) or death due to any cause.

Subjects who do not experience disease progression and are alive on or before the data cut-off date will be censored at the time of last evaluable tumor assessment or data cut-off date, whichever is earlier. Subjects who do not experience disease progression and start new systemic anti-cancer therapy will be censored at the last evaluable tumor assessment on or prior to the time the new systemic anti-cancer therapy was begun or the data cut-off date, whichever is earlier. For analyses conducted in the FAS, subjects with no evaluable post-baseline tumor assessments will be censored at the time of receipt of first study drug. Subjects who are lost to follow-up for assessment of disease progression will be censored at their last evaluable tumor assessment or data cut-off date, whichever is earlier. The analysis of PFS will be performed in the EAS using Kaplan-Meier methods. Analyses may be repeated in the FAS.

Duration of response (DOR) includes subjects with an objective disease response (PR or CR) and is defined as the time from the first tumor assessment that supports the subject's objective

disease response to the time of disease progression or death due to any cause. Subjects who do not experience disease progression or death at the time of analysis will be censored using the same rules as described for PFS. The analysis of DOR will be performed in the EAS using Kaplan-Meier methods.

Overall Survival (OS) defined as the time from first dose of study drug until date of death due to any cause. Subjects without documentation of death at the time of analysis will be censored as of the date the subject was last known to be alive, or the data cut-off date, whichever is earlier. OS will be performed in the FAS using Kaplan-Meier methods. The analysis may be repeated in the SAF.

6.5.5.3 Exploratory Variables and Analysis

Exploratory efficacy analyses will be evaluated based on the following variables:

- ORR, DCR, DOR and PFS using irRECIST ([Nishino, 2013](#))
- Association of PD-L1 expression with clinical efficacy
- Association of mesothelin expression in tumor tissue with clinical efficacy

Additional efficacy analyses that may be evaluated include:

- Association of immunological responses with clinical efficacy
- Association with circulating and molecular biomarkers with clinical efficacy
- Impact of EBV status and other molecular characteristics including but not limited to human epidermal growth factor receptor 2 (HER2) status, MSI, and chromosomal instability (CIN), on clinical efficacy
- Association of molecular characteristics including but not limited to HER2 status and IFN-related gene signature with clinical efficacy

Exploratory analyses of the data will be conducted as deemed appropriate. Details of additional analysis of other variables are provided in the SAP.

6.5.6 Safety Analyses

AEs will be coded according to the Medical Dictionary for Regulatory Activities (MedDRA) version 18.1 or higher and assessed for severity using the NCI-CTCAE v. 4.03. The number and percentage of subjects experiencing any TEAE, overall, and by system organ class and preferred term will be tabulated. The incidence rates adjusted by cumulative exposure will also be presented overall and by cycle. AEs associated with clinical laboratory parameters will be characterized according to NCI CTCAE, Version 4.03. Shifts in toxicity grades from baseline to each visit will be summarized.

6.5.7 Research Laboratory Analyses

Analyses of research laboratory samples, tumor biopsies, and immune response data will be described separately outside the context of the SAP.

6.5.8 Timing of Analysis

The final analysis will be performed after all subjects have completed at least 6 cycles of treatment or discontinued study treatment and completed the EOT Visit. A supplemental analysis may be completed at the end of study that includes the cumulative data collected after the final analysis (i.e. through the Follow-up Period).

6.5.9 Data Monitoring Committee

There will be no formal Data Monitoring Committee for this study. Safety data and all unacceptable toxicities will be reviewed by the SRT comprised of participating investigators in the study, the Medical Monitor, and representatives of the Sponsor.

7 ADVERSE EVENT REPORTING AND FOLLOW UP

7.1 Adverse Events

An AE is defined as any untoward medical occurrence associated with the use of a drug in humans, whether or not considered drug related. An AE can therefore be any unfavorable and/or unintended sign (including an abnormal laboratory finding), symptom, or disease temporally associated with the use of an investigational medicinal product, whether or not related to the investigational medicinal product. All AEs, including observed or volunteered problems, complaints, or symptoms, are to be recorded on the appropriate eCRF.

AEs occurring from the time of first study drug administration and up to 28 days after the last dose of study drug or until a subject initiates a new cancer therapy, whichever is earlier, will be monitored and documented on the AE eCRF. AEs include clinical laboratory test variables and events observed by the Investigator; subjects should be instructed to report any AE that they experience to the Investigator. At each indicated visit, Investigators should make an assessment for AEs and record the event on the appropriate AE eCRF.

Wherever possible, a specific disease or syndrome rather than individual associated signs and symptoms should be identified by the Investigator and recorded on the eCRF. However, if an observed or reported sign or symptom is not considered a component of a specific disease or syndrome by the Investigator, it should be recorded as a separate AE on the eCRF. Additionally, the condition that led to a medical or surgical procedure (e.g. surgery, endoscopy, tooth extraction, or transfusion) should be recorded as an AE, not the procedure.

Any medical condition already present prior to the first dose of study drug should be reported in medical history unless the medical condition or signs or symptoms present at baseline change in severity or seriousness at any time during the study. In this case, it should be reported as an AE.

Clinically significant abnormal laboratory or other examination (e.g. ECG) findings that are detected during the study or are present at screening and significantly worsen during the study should be reported as AEs. The Investigator will exercise his or her medical and scientific judgment in deciding whether an abnormal laboratory finding or other abnormal assessment is clinically significant. Clinically significant abnormal laboratory values occurring during the clinical study will be followed until repeat tests return to normal, stabilize, or are no longer clinically significant. Any abnormal test that is determined to be an error does not require reporting as an AE.

Examples of AEs include the following:

- Significant or unexpected worsening or exacerbation of the indication under study
- Exacerbation of a chronic or intermittent preexisting condition, including an increase in frequency or intensity of the condition

- New conditions detected or diagnosed after investigational agent administration even if they were present before the start of the study
- Signs, symptoms, or the clinical sequelae of a suspected interaction with another medical product
- Signs, symptoms, or the clinical sequelae of a suspected overdose of either investigational agent or a concurrent medication.

An overdose should not be reported as an AE or SAE; instead, the symptoms resulting from the overdose should be reported as the AE or SAE.

Examples of AEs do not include the following:

- Medical or surgical procedures (e.g. endoscopy, appendectomy); instead, the medical condition that led to the procedure is an AE
- Situations that are unwanted but in which an untoward medical occurrence did not occur (e.g. social inconvenience after admission to a hospital)
- Anticipated day-to-day fluctuations of a pre-existing disease or condition (present or detected before enrollment) that does not worsen overall

A follow-up is required for all subjects with AEs until the event has been resolved or the condition has stabilized. In case of unresolved AEs, including significant abnormal laboratory values at the EOT visit assessment, these events will be followed up until resolution or until they become clinically not relevant.

7.1.1 Disease Progression and Other Events of Clinical Interest

7.1.1.1 Disease Progression

Progression of the cancer under study is not considered an AE in this study unless it is considered to be drug-related by the investigator. The term "disease progression" should be recorded as an AE/SAE only if there are no other identifiable AEs/SAEs associated with the disease progression at the time of reporting. For events associated with disease progression, the relevant signs and symptoms should be reported using a diagnosis whenever possible rather than individual underlying signs and symptoms. When a clear diagnosis cannot be identified, each sign or symptom should be reported as a separate AE. If the events resulting from disease progression meet the criteria for an SAE (e.g. resulted in hospitalization, a life-threatening event, or death), the specific event(s) should be reported as an SAE(s). In both cases (i.e. AEs or SAEs related to disease progression), it should be indicated that each event (reported as a diagnosis or as signs and symptoms) is related to disease progression on the AE eCRF.

7.1.1.2 Events of Clinical Interest

[REDACTED]

Drug-Induced Liver Injury

Serum chemistry laboratory values consistent with Hy's Law criteria (i.e. all 3 of the following must coexist):

- ALT or AST $\geq 3 \times$ ULN
- Total bilirubin $\geq 2 \times$ ULN
- ALP $< 2 \times$ ULN

Laboratory values meeting all criteria for potential Hy's Law cases from the time of first study drug administration through the EOT visit are considered ECI and should be reported following SAE reporting procedures ([Section 7.3](#)).

7.1.2 Assessment of Adverse Events by the Investigator

The Investigator will assess the severity (intensity) of each AE and the potential relationship between the AE and the study medication.

Assessment of Severity:

The severity of all AEs should be graded according to the NCI-CTCAE v. 4.03 (<http://ctep.cancer.gov/reporting/ctc.html>). For AEs not listed in the CTCAE, the following grading system should be used:

- Mild (CTCAE Grade 1): Transient symptoms, awareness of sign/symptom, but easily tolerated and no interference with subject's daily activities
- Moderate (CTCAE Grade 2): Marked signs/symptoms that interfere with subject's usual activities, but still acceptable
- Severe (CTCAE Grade 3): Incapacitating signs/symptoms which cause considerable interference with the subject's daily activities, unacceptable
- Life-threatening (CTCAE Grade 4): Life-threatening or disabling AE
- Death (CTCAE Grade 5): Death-related AE

Attribution:

The Investigator is obligated to estimate the relationship between the investigational agents and the occurrence of each AE or SAE using best clinical judgment. Other causes, such as the underlying disease, concomitant therapy, other risk factors, and the temporal relationship of the

event to the investigational agents should be considered and investigated. The Investigator should consult the IB or product labeling information for marketed products in the determination of the assessment. The Investigator should consider all possible etiologies for the AE and render a causality assessment based on the most likely contributing factor to the AE.

There may be situations when an SAE has occurred and the Investigator has minimal information to include in the initial report. However, the Investigator must assess causality for every event before the transmission of the SAE. The Investigator may change his or her opinion of the causality in light of follow-up information, amending the SAE report.

The assessment of the relationship between the AE and the study medication will be determined using one of the following attribution categories as outlined in the NCI Guidelines: Adverse Event Reporting Requirements (2013).

RELATIONSHIP	ATTRIBUTION	DESCRIPTION
Unrelated to investigational agent/intervention	Unrelated	The AE is clearly NOT related to the intervention
	Unlikely Related	The AE is doubtfully related to the intervention
Related to investigational agent/intervention	Possibly Related	The AE may be related to the intervention
	Probably Related	The AE is likely related to the intervention
	Definitely Related	The AE is clearly related to the intervention

AEs listed as possibly, probably, or definitely related are considered to have a suspected “reasonable causal relationship” to the investigational agent/intervention (ICH E2A). The expression “reasonable causal relationship” is meant to convey in general that there are facts (evidence) or arguments to suggest a causal relationship

7.2 Serious Adverse Events

An AE or adverse reaction is considered serious if, in the view of either the Investigator or Sponsor, it results in any of the following outcomes:

- Death
- A life-threatening AE
 - NOTE: An AE or adverse reaction is considered “life-threatening” if, in view of either the Investigator or Sponsor, its occurrence places the subject at immediate risk of death. It does not include an event that, had it occurred in a more severe form, might have caused death.

- Requires hospitalization or prolongation of existing hospitalizations;
 - NOTE: Any hospital admission with at least 1 overnight stay will be considered an inpatient hospitalization. An emergency room visit without hospital admission will not be recorded as an SAE under this criterion, nor will hospitalization for a procedure scheduled or planned before signing of informed consent. However, unexpected complications and/or prolongation of hospitalization that occur during elective surgery should be recorded as AEs and assessed for seriousness. Admission to the hospital for social or situational reasons (i.e. no place to stay, live too far away to come for hospital visits) or for observation post-study drug administration will not be considered a SAE.
- A persistent or significant disability/incapacity or substantial disruption of the ability to conduct normal life functions
- A congenital anomaly/birth defect; or
- An important medical event
 - NOTE: Important medical events that may not result in death, be life-threatening, or require hospitalization may be considered an SAE when, based upon appropriate medical judgment, they may jeopardize the subject and may require medical or surgical intervention to prevent one of the outcomes listed above. Examples of such medical events include allergic bronchospasm requiring intensive treatment in an emergency room or at home, blood dyscrasias or convulsions that do not result in inpatient hospitalizations, or the development of drug dependency.

7.3 Serious Adverse Event Reporting – Procedures for Investigators

7.3.1 Initial Reports

SAEs will be collected from the time of first study drug administration through 90 days following cessation of treatment, or 28 days following cessation of treatment if the subject initiates new anticancer therapy, whichever is earlier. SAEs and events of clinical interest must be reported to the Sponsor (or designee) within 24 hours of the knowledge of the occurrence. Outside of the 90-day period, only SAEs considered related to the administration of study drug must be reported to the Sponsor.

In the event an SAE is observed or reported, the SAE report will be completed as thoroughly as possible including all available details about the event and the signature of the Investigator. If the Investigator does not have all information about an SAE, the Investigator will not wait to receive additional information before notifying the Sponsor of the event and completing the form. The form will be updated when additional information is received.

Complete the paper SAE form for each SAE. The SAE form will be faxed or emailed to the Sponsor or designee within 24 hours of awareness of the initial or any follow-up information, and designated study personnel will be notified electronically. If the SAE falls on a weekend or

holiday, an email notification is acceptable but must be followed by an SAE reporting form on the next business day.

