6.4.1.3 Archived Tumor Tissue and Tumor Biopsies

Archived tissue from the primary tumor will be collected for all enrolled subjects to assess expression of PD-L1 and mesothelin by immunohistochemistry (IHC). Archived samples should be submitted with a pathology report; personal identifying information must be redacted. If archival primary tumor tissue from the original diagnostic formalin-fixed paraffin-embedded block is not available, tissue from metastatic site is acceptable if primary site is not accessible for biopsy.

Paired tumor biopsies of primary tumor or a metastatic site for pre-treatment and on Cycle 2 Day 15 will be collected to evaluate changes in PD-L1 and mesothelin status, as well as any cellular or genomic changes in markers of immune response or disease status. If at Cycle 2 a subject's tumor is thought to be unsafe for biopsy by the Investigator, the site must discuss with the Medical Monitor to determine if an alternative acceptable method may be allowed.

An image assisted core needle biopsy using standard techniques will be obtained from the primary tumor site(s) and/or accessible metastatic lesions. The tissue sample should have proper size to enable IHC analysis of PD-L1 and mesothelin. Fine needle aspirations will not be acceptable.

Paired biopsies will be collected 1) any time between screening and prior to the first dose of study medication (baseline) and 2) during treatment (Cycle 2 Day 15 post CRS-207/pembrolizumab administration). Cycle 2 Day 15 biopsy should not be collected until at least seven (7) days have passed since CRS-207 administration, but no later than Day 15 of cycle to allow sufficient recovery time prior to CRS-207 administration. An additional biopsy may be requested at the EOT visit. If additional biopsies or relevant samples (e.g. pleural fluid) are collected for routine care during the course of study, a sample should be retained if possible for Sponsor research evaluation. Detailed instructions for tissue collection, processing and shipment are provided in the Laboratory Manual.

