6.4.3.3 Physical Examination and Weight

Comprehensive Physical Examination

Complete physical examinations will be conducted at screening and EOT. Comprehensive physical examinations must be performed by a medically qualified individual such as a licensed Physician, Physician's Assistant, or an advanced Registered Nurse Practitioner, as local law permits. The comprehensive physical examination will include the following organ or body

system assessments: skin; head, eyes, ears, nose, and throat; thyroid; lungs; cardiovascular system; abdomen (liver and spleen); extremities; lymph nodes; and a brief neurological examination. Before the first dose of study drug, clinically significant abnormal findings should be recorded as medical history. After the first dose of study treatment, new clinically significant abnormal findings should be recorded as AEs.

Symptom-directed Physical Examination

Symptom-directed physical examinations will be conducted at all other indicated visits (up to 3 days prior to dosing). The Investigator or medically qualified designee will perform a symptom-directed evaluation as clinically indicated. The targeted physical examination will include assessment(s) of the body systems or organs, as indicated by subject symptoms, AEs, or other findings. New clinically significant abnormal findings should be recorded as AEs.

Weight

Weight will be obtained at each indicated visit, and prior to receiving any study medication.

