6.4.3.4 Adverse Events

AEs will be recorded from the time of first study drug administration until 28 days following the last dose of study drug or initiation of subsequent cancer-related therapy, whichever occurs first. SAEs should be reported per the timeframe and procedures described in [Section 7.3](#). If the EOT visit occurs less than 28 days from the last dose of study drug, the subject will be contacted by telephone 28 days (+ 3 days) after the date of last study drug administration to complete the AE reporting period. A follow-up contact for AEs will also be conducted 1 day after each CRS-207 infusion (and one day after pembrolizumab infusions beyond Cycle 5 where CRS-207 is not administered). Contact must be documented in the study records.

All AEs and abnormal clinical laboratory assessments will be assessed for severity using the NCI-CTCAE v. 4.03. The determination, evaluation, reporting, and follow-up of AEs will be performed as outlined in [Section 7](#).

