10.1. Adverse Events

AEs will be recorded from the time of first study drug administration until 28 days after the last dose of study drug or until a subject initiates a new cancer therapy, whichever is earlier. AEs will also be assessed for severity using the NCI-CTCAE v. 4.03, relationship to each therapy (Definitely Related, Probably Related, Possibly Related, Unlikely Related, Not Related), and seriousness (Yes, No). AEs will be considered treatment-emergent if their onset occurs within the on-therapy period. Summary of events related to any study treatment will be provided.

Sponsor: Aduro Biotech, Inc.
Protocol Number: ADU-CL-14
Version and Date: Version 1.0, 13Mar2018

An overview of treatment-emergent AEs (TEAEs) will be produced, including counts and percentages of subjects with any incidences of: TEAEs, CTCAE Grade 3 or higher TEAEs, TEAEs related to study treatment, CTCAE Grade 3 or higher TEAEs related to study treatment, serious adverse events (SAEs), TEAEs leading to study drug discontinuation, infusion-related reactions (IRRs), and fatal TEAEs.

A separate overview of AEs identified as IRRs related to CRS-207 will be provided. This display will include the number of infusions received by subjects, the number of subjects having an IRR, total number of IRRs per subject, maximum IRR grade, and dose modifications resulting from IRRs.

Adverse events will be coded based on the Medical Dictionary for Regulatory Affairs (MedDRA) for reporting by system organ class (SOC) and preferred term (PT) in descending order of overall incidence. For these summaries, subjects with multiple AEs with the same SOC and/or PT will only be counted once at each level of summarization.

Summaries of adverse events by SOC and PT will include the following types:

- TEAEs;
- TEAEs related to any study treatment (Definitely Related, Probably Related, or Possibly Related);
- CTCAE Grade 3 or higher TEAEs;
- CTCAE Grade 3 or higher TEAEs related to any study treatment;
- CRS-207 infusion-related reactions;
- SAEs.

To account for potential differences in the extent of exposure between the treatment categories, a subject-year adjusted rate will also be presented. The rate is calculated as the number of subjects with an event divided by the total subject-years of safety observation, where subject-years of safety observation for each subject is defined as duration of safety observation (defined in Section 5.3) in days divided by 365.25.

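### Safety collection opens at first dose, so a serious complication confined to the period between the mandatory pre-treatment biopsy and first dose is not reported as an AE or SAE

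*Protocol*

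**What the plan says.** **Start of collection.** For SAEs, Protocol 7.3.1 reads "SAEs will be collected from the time of first study drug administration". For AEs, Protocol 6.4.3.4 reads "AEs will be recorded from the time of first study drug administration until 28 days following the last dose of study drug"; Protocol 7.1 and SAP 10.1 use the same starting point.

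**Events outside the SAE window.** Protocol 7.3.1 adds: "Outside of the 90-day period, only SAEs considered related to the administration of study drug must be reported to the Sponsor".

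**Conditions that arise before dosing.** Protocol 7.1: "Any medical condition already present prior to the first dose of study drug should be reported in medical history". Such a condition becomes an AE only if its severity or seriousness changes during the study. Protocol 6.4.3.3 treats examination findings in the same way: "Before the first dose of study drug, clinically significant abnormal findings should be recorded as medical history".

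**The biopsy.** Inclusion criterion 8 (Protocol 6.2.1) asks for a pre-treatment biopsy of the primary tumor or a metastasis, and the Synopsis calls the paired biopsies required. Protocol 6.4.1.3 specifies an image-assisted core needle technique, rules out fine needle aspiration, and places the first biopsy at "any time between screening and prior to the first dose of study medication (baseline"). The stated purpose is PD-L1, mesothelin and other cellular or genomic markers.

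**The concern.** The first biopsy is invasive, is required for entry and serves the trial's research aims. By design it falls before the point at which any adverse event is collected. A consented subject admitted to hospital with a bleed or perforation from that biopsy has been harmed by a trial procedure, but the protocol asks for no SAE form and no 24-hour notice.

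What is at stake is participant safety, not an efficacy estimate. The trial has no formal data monitoring committee; safety data go to the Safety Review Team (Protocol 6.5.9). Without a report, that team and the Sponsor have no defined route to learn of a biopsy complication while further subjects are being biopsied. Nor could the trial later state the risk of its paired-biopsy requirement, because only the on-treatment half is counted.

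**Working it through.** The plan states no figure on this point, so there is none to reproduce. The check is a comparison of texts, followed by an illustration of scale.

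**Step 1: order of events.** The first biopsy precedes first dose (Protocol 6.4.1.3). AE and SAE collection begins at first dose (Protocol 6.4.3.4, 7.1, 7.3.1; SAP 10.1). Screening must be completed within 28 days before first dose (Protocol 6.4), so the uncovered period is up to 28 days.

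**Step 2: does another rule cover the interval?**
- The out-of-window rule in Protocol 7.3.1 reaches only SAEs related to study drug. A procedure complication before any drug cannot qualify.
- Protocol 7.2 has complications of elective surgery recorded as AEs and assessed for seriousness, but it does not move the start of collection.
- SAP 5.4 defines a pre-therapy period, but SAP 10.1 still starts AE recording at first dose.
- The visible text of Protocol 7.1.1.2 also counts potential Hy's Law cases from first dose. Part of that section is redacted, so this check covers the visible text only.

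No visible rule in either document collects events from consent, or events caused by required procedures.

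**Step 3: where the complication is recorded.**

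| Situation | Record under the plan | SAE form and 24-hour report if serious |
|---|---|---|
| Pre-dose onset, subject dosed, no later change | Medical history (Protocol 7.1, 6.4.3.3), listed under SAP 6.5 | No |
| Pre-dose onset, changes in severity or seriousness after dosing | AE (Protocol 7.1) | Yes |
| Pre-dose onset, subject never dosed | Reason for ineligibility (Protocol 6.4.1.4); screen-failure listing (SAP 6.2); outside the Safety Set (SAP 6.1) | No |
| Onset after the Cycle 2 Day 15 biopsy | AE | Yes |

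The first and third rows are the gap.

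**Step 4: scale, for illustration.** Inputs: n = 79 planned subjects (Protocol 6.5.1) and a serious complication rate p per biopsy. The documents give no p, so the values are assumptions. Expected events = n × p. Chance of at least one = 1 − (1 − p)^n, taking subjects as independent with a common p.

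| Assumed p | Expected events | Chance of at least one |
|---|---|---|
| 0.5% | 79 × 0.005 = 0.4 | 1 − 0.995^79 = 33% |
| 1% | 79 × 0.01 = 0.8 | 1 − 0.99^79 = 55% |
| 2% | 79 × 0.02 = 1.6 | 1 − 0.98^79 = 80% |
| 3% | 79 × 0.03 = 2.4 | 1 − 0.97^79 = 91% |

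These are chances that an event occurs, not that one goes unreported. Events in the second row of the Step 3 table would be reported. Subjects biopsied but never dosed would add to n; subjects whose first biopsy was standard of care would reduce the part due to the trial.

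**The case against.** The strongest defence is that the first-dose start is a consistent design choice. It is the same in three protocol sections and the SAP, it fits the drug-based AE definition in Protocol 7.1, and neither document states a standard that requires collection from consent. That is fair: this is not a contradiction between passages. But consistency does not supply a report for harm from a procedure that the trial itself requires.

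Several stronger readings are tempting, and the documents do not support them.

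- **That such complications are never captured.** A complication that begins or worsens after dosing becomes an AE (Protocol 7.1), and a stable one in a dosed subject is recorded and listed as medical history.
- **That no record exists for subjects never dosed.** The reason for ineligibility is documented and screen failures are listed. What is missing is the AE or SAE record with its 24-hour report.
- **That an unresolved injury is hidden just before a live bacterial agent is given.** Exclusions 9 (recent transfusion), 10 (active infection requiring systemic therapy), 24 (clinically significant intercurrent illness) and 29 (unhealed wound) stand in the way. Table 1-1 repeats the eligibility review on Cycle 1 Day 1, with examination, vital signs and hematology. Grade 3 or higher laboratory abnormalities need Medical Monitor approval before enrollment (Protocol 6.2.1), and the Sponsor or designee approves each enrollment form (Protocol 6.4.1.4). These controls limit the dosing risk. They do not create a safety report, and by keeping an injured subject from dosing they may move the event into the group with the thinnest record.
- **That every first biopsy is due solely to the trial.** Protocol 6.4.1.1 lets standard-of-care assessments within the screening period be used, so some may not be.

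A last objection is timing. SAP 3.5 records that development of CRS-207 ceased and that every subject had completed the end-of-treatment visit by 31 January 2018; the SAP is dated 13 March 2018. An SAP change alone could show nothing systematic that the protocol had not collected. That stands.

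**Conclusion.** The point holds in a bounded form. Following the plan exactly, a serious complication of the required pre-treatment biopsy needs no SAE form or 24-hour report if it begins before first dose and does not later change in severity or seriousness. The gap is widest for subjects never dosed. The matched biopsy at Cycle 2 Day 15 is covered, so the safety record of the paired procedure is one-sided.

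The conclusion rests on the visible wording, not on the assumed complication rates. Those rates suggest anything from an unlikely single event to two or three among 79 subjects, and the documents cannot narrow that range or say what share would go unreported. ORR and the other efficacy endpoints are unaffected, as are the TEAE tables. The gap should be closed because it concerns harm from a trial requirement and costs little to close.

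**What to change.** In Protocol 6.4.3.4, 7.1 and 7.3.1, collect SAEs, and AEs related to protocol-mandated procedures, from signed informed consent to first dose. Apply the same 24-hour reporting to these SAEs, and state that the rule includes consented subjects who are never dosed. Keep the first-dose start for all other AEs.

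In the SAP, add one listing of pre-therapy procedure-related events, using the pre-therapy period already defined in SAP 5.4. It must not be limited to the Safety Set, and it stays outside the TEAE tables. The listing is useful only if the protocol collects the data; for this trial, now closed out, it could show only what is already on record.

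Cost: wording in three protocol sections, a few more SAE forms and one listing. No added visits or procedures, and no change to the TEAE definition or tables.
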